### **Partial Response**

PR requires all of the following for a period of at least 4 weeks (**NOTE:** PR does not require bone marrow examination):

The patient must have the following (if abnormal prior to treatment):

- $\geq 50\%$  decrease or normalization ( $<5.0 \times 10^9/L$ ) in peripheral blood lymphocyte count from the pretreatment baseline value,
- $\geq 50\%$  reduction in lymphadenopathy by CT or MRI, based on sum of products of perpendicular diameters, or resolution to size consistent with CR,
- $\geq 50\%$  reduction in abnormal hepatosplenomegaly by CT or MRI, or resolution to size consistent with CR,
- Neutrophils  $\geq 1.5 \times 10^9/L$  or 50% improvement over baseline without growth factors for at least 4 weeks,
- Platelets  $\geq 100 \times 10^9/L$  or 50% improvement over baseline, and
- Hemoglobin  $\geq 11.0$  g/dL or 50% improvement over baseline without transfusions or growth factors for at least 4 weeks. For patients who are transfusion-dependent at baseline, a hemoglobin of  $\geq 9.0$  g/dL without transfusions or growth factors for at least 4 weeks.

- The beginning of PR will be considered the beginning of the 4-week duration of required blood counts meeting PR criteria.

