## **5.2 General Concomitant Medication and Supportive Care Guidelines**

### **5.2.1 Concomitant Medications**

Subjects may receive medications as supportive care or to treat AEs as deemed necessary by the investigator or the subject's physician.

All concomitant medications given to the subject from the time the subject signs the informed consent form through 181 days after end of treatment of moxetumomab pasudotox will be recorded on the source document. Beyond 181 days after the end of treatment of moxetumomab pasudotox until end of study, only administrations of blood component transfusions and hematopoietic growth factors will be recorded.

Subjects should continue to take their usual chronic maintenance medications (such as antihypertensives, thyroid replacement therapy, vitamin or mineral supplements) during the course of the study other than those contraindicated by the inclusion/exclusion criteria.

Instructions for specific medications are listed below:

1. Prophylactic use of hematopoietic growth factors, such as filgrastim, sargramostim, or pegfilgrastim, is permitted when IV antibiotics are given for fever ( $> 38.0^{\circ}\text{C}$ ) and neutropenia ( $< 0.5 \times 10^9/\text{L}$ ). Use at the discretion of the study principal investigator (PI) for Grade 4 neutropenia without fever is permitted but discouraged.
2. Concurrent chemotherapy, radiotherapy, immunotherapy, biologic, and hormonal therapy for treatment of cancer during the study are not permitted.
3. Use of steroids is not routinely recommended to prevent CLS or fever from moxetumomab pasudotox; however, secondary prophylaxis for infusion-related reactions with dexamethasone 4 mg IV or oral may be administered at the investigator's discretion.
4. Use of NSAIDs is not permitted from the first dose of the cycle through 7 days after the last dose of the cycle.

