### **5.2.2.2 Blood Product Support**

Symptomatic anemia should be treated with appropriate red blood cell (RBC) support. Transfusion is generally recommended if the hemoglobin falls below 8g/dL, but lower levels are acceptable particularly for younger patients. Platelets are generally given when the platelet count is  $< 10 \times 10^9/\text{L}$  or when there is bleeding.

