#### Complete Response with or without Minimal Residual Disease

CR  $\pm$  MRD requires all of the following to be present:

- No evidence of leukemic cells in the peripheral blood and/or by routine H/E staining of bone marrow. Minimal Residual Disease: CR with HCL evident in blood or marrow by flow cytometry or in bone marrow biopsy by immunohistochemistry (**NOTE:** A second confirmatory bone marrow examination is not required).

- Resolution of any hepatomegaly, splenomegaly, and abnormal ( $\geq 2$  cm minimum length) lymphadenopathy by CT or MRI. Although a normal spleen size is not defined, the maximum diameter of the spleen should be either  $< 17$  cm or have decreased by  $>25\%$  from its baseline.
- Normal CBC as exhibited by: Neutrophils  $\geq 1.5 \times 10^9/L$ , Platelets  $\geq 100 \times 10^9/L$ , and Hemoglobin  $\geq 11.0$  g/dL without transfusions or growth factors for at least 4 weeks.

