#### **13.4.1.2 Objective Response Rate**

Objective response rate is defined as the proportion of subjects with CR or PR. The 95% CIs of ORR will be estimated using the exact probability method.

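### The partial-response platelet criterion is the only blood-count line with no transfusion- or growth-factor-free condition, so a supported platelet count can help to qualify a patient for PR and ORR

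*Protocol*

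**What the plan says.** The PR definition in Protocol 11.1 opens with "PR requires all of the following for a period of at least 4 weeks". Each item applies only where the value was abnormal before treatment. The three blood-count lines then differ:

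- **Neutrophils:** at least 1.5 × 10⁹/L "or 50% improvement over baseline without growth factors for at least 4 weeks".
- **Platelets:** at least 100 × 10⁹/L "or 50% improvement over baseline, and". Nothing follows about support.
- **Hemoglobin:** at least 11.0 g/dL "or 50% improvement over baseline without transfusions or growth factors for at least 4 weeks", with a separate threshold for patients who were transfusion-dependent at baseline.

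For CR, also in 11.1, neutrophils, platelets and hemoglobin stand in one sentence that closes with "without transfusions or growth factors for at least 4 weeks".

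Platelet transfusion is foreseen. Section 5.2.2.2 says "Platelets are generally given when the platelet count is" below 10 × 10⁹/L, or when there is bleeding. Under 13.4.1.2, "Objective response rate is defined as the proportion of subjects with CR or PR".

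**The concern.** The three PR lines run in parallel, and two of them guard against a count that reflects supportive care and not disease response. The third does not. In CR the same guard covers all three counts. Nothing in the protocol suggests that platelets were meant to be treated differently in PR, and nothing elsewhere excludes a transfused platelet value from the PR assessment.

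Patients who could be affected are eligible. Platelets below 100 × 10⁹/L are one route into the trial (3.1.1). Exclusion 16 admits counts below 50 × 10⁹/L when the investigator attributes them to the disease (3.1.2).

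What is at stake is the ORR, a named secondary objective (1.2). The trial has a single arm, so no control group would share the misclassification.

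**Working it through.** **1. The plan's own design figure.** Section 13.5 states 90% power with 77 subjects for durable CR of 28% against 13%, two-sided 0.05. The exact one-sample binomial test rejects at 17/77 or more. The upper-tail error is P(X ≥ 17 | 0.13) = 0.0189 and the power is P(X ≥ 17 | 0.28) = 0.903. The stated 90% reproduces. Durable CR rests on the CR counts, which already carry the support-free condition, so this point does not change N or power.

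**2. When can a supported platelet count satisfy the PR line?** The improvement route requires at least 1.5 × baseline, held for 4 weeks. Under the count trigger in 5.2.2.2, a repeatedly transfused patient falls below 10 × 10⁹/L each time.

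| Baseline (× 10⁹/L) | Needed (1.5 × baseline) | Do values just below 10 meet it? |
|---|---|---|
| 10 | 15 | No |
| 8 | 12 | No |
| 6.7 or less | 10 or less | Can do |

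The limit comes from 1.5 × baseline ≤ 10, so baseline ≤ 6.7. Above that baseline, three routes remain:

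- transfusion for bleeding, which 5.2.2.2 ties to no count;
- transfusion outside the general practice that 5.2.2.2 describes;
- low values that go unmeasured or are disregarded. Section 11.1 lets the investigator ignore isolated values, and values in the first 12 days of a cycle.

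**3. Effect on ORR.** One patient is 1/77 = 1.3 points, three are 3/77 = 3.9 and five are 5/77 = 6.5. For illustration only, take starting rates near the 72–81% ORR that section 2.2 gives for the precursor agent, with Clopper-Pearson 95% intervals. The number removed (0 to 5) is an assumption.

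| PRs removed | From 55/77 | From 62/77 |
|---|---|---|
| 0 | 71.4% (60.0–81.2) | 80.5% (69.9–88.7) |
| 1 | 70.1% (58.6–80.0) | 79.2% (68.5–87.6) |
| 3 | 67.5% (55.9–77.8) | 76.6% (65.6–85.5) |
| 5 | 64.9% (53.2–75.5) | 74.0% (62.8–83.4) |

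**4. Direction for the other endpoints.**

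- *Time to response* (13.4.1.3) is summarised in responders only. An earlier credited response shortens it, and an added responder can move the summary either way.
- *Duration of response* (13.4.1.4) could shorten, if a supported PR is fragile, or lengthen, if support hides its loss.
- *PFS and TTF* (13.4.1.5, 13.4.1.6) use relapse from best response. Moving a patient from stable disease to PR replaces the progression criteria with the loss of any PR criterion. That tends to bring events forward, while continued support could delay them.

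**The case against.** The best case against this point is that the rest of the PR definition leaves little room for a false response.

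- **The 4-week rule and the transfusion trigger work together.** A reader might infer that going from 10 to 15 × 10⁹/L by transfusion is enough, or that the 4-week rule offers no protection because transfusions are repeated. Neither follows. As step 2 shows, a patient who keeps falling below 10 does not hold 15 for 4 weeks, and recurrent low values are not isolated values. This part of the objection stands and narrows the point.
- **All applicable items must be met together.** A patient with abnormal baseline hemoglobin must also meet that line free of transfusions, a word that is not limited to red cells. Section 2.1 describes HCL patients as presenting with pancytopenia, so many platelet-supported patients would face this test. That also stands, but it does not cover a patient whose baseline hemoglobin was normal.
- **The hemoglobin condition might be read back onto platelets.** The lines are separate bullets, and the neutrophil bullet has its own, different condition. If the last bullet governed all three, that condition would be largely redundant. At best the text is ambiguous, and one phrase would still be needed.
- **Response is centrally reviewed, and ORR is only estimated.** Both are true. But without a written rule, central review has no stated basis for discounting a supported count.

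A reader might also infer that neutrophils carry a transfusion-free condition. They do not; theirs concerns growth factors only.

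**Conclusion.** The inconsistency is real. The PR platelet line alone lacks a support-free condition, and a supported platelet count can satisfy that component if everything else required for PR holds for 4 weeks. ORR could then be overstated by 1.3 points per affected patient, on a denominator of 77.

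The documents do not support a stronger statement. They give no frequency of platelet transfusion around assessment, so any assumed share of patients would yield at most a ceiling: each transfused patient must still meet all the other PR items. The number affected may be zero or few. Nor do the documents establish that time to response, duration of response, PFS or TTF would look better, since the effect could go either way. The primary endpoint is untouched. This should be corrected because it is clear and cheap to correct, and because deciding who counts as a responder after seeing the data would be worse.

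**What to change.** In the PR platelet line of 11.1, add the wording already used for the CR counts and for PR hemoglobin: "without transfusions or growth factors for at least 4 weeks". Make the same change in the central review charter, and name transfusion and growth-factor records among the documents sent to the central vendor under 13.3.

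The information is already required. Section 5.2.1 records all concomitant medication through 181 days after end of treatment. After that, until end of study, "only administrations of blood component transfusions and hematopoietic growth factors will be recorded". Table 10-2 carries the same rule for the later visits.

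The cost is one phrase in the protocol and one in the charter. ORR may become slightly less favourable. Sample size, power and the primary analysis do not change.

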**Table 10-2 Study Calendar for End of Treatment and Follow-up**

Evaluation/Intervention	EOT a	From end of treatment assessment					Yearly Thereafter (± 1M)
		Every month for 6 months (if in CR) (± 1W)	Every 3 months for 24 months (± 2W)	181D (+ 2W)	12 months (± 1M)	18 months (± 1M)	
[REDACTED]	■			■	■	■	■
[REDACTED]	■			■			

AlkPhos = alkaline phosphatase; ALT = alanine transaminase; AST = aspartate aminotransferase; BM = bone marrow; BUN = blood urea nitrogen; CBC= complete blood count; CK = creatinine kinase; CR = complete response; CRP = C reactive protein; CT = computed tomography; D = day; ECG = electrocardiogram; EOT = end of treatment; GGT = gamma-glutamyl transferase; LDH = lactate dehydrogenase; M = month; MRI = magnetic resonance imaging; PT = prothrombin time; PTT = partial thromboplastin time; TSH = thyroid stimulating hormone; W = week.

- a End of treatment is 28-42 days after the first dose of the last cycle. At the discretion of the investigator, a full disease assessment may be performed prior to completion of 6 cycles of therapy if the patient maintains blood counts needed for CR for at least 4 weeks. This interim assessment will include all assessments required at EOT.
- b Only to collect blood component transfusions and hematopoietic growth factors uses.
- c CT or MRI abdomen at 6 and 18 month time points after EOT. Subjects enrolled in Germany will utilize MRI for all radiographic assessments (CT not permissible).
- d This assessment is required 6 months after EOT only for patients in CR or PR.
- e Patients in CR will have a CBC with differential (no peripheral blood smear) monthly from the EOT assessment until the 181D assessment, then every 3 months for 24 months, then every 6 months thereafter. For patients not in CR, repeat CBC with differential (no peripheral blood smear) every 3 months for 24 months after the end of treatment, and every 6 months thereafter.

[REDACTED]

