## 11 MEASUREMENT OF EFFECT

For the purposes of this study, patients will receive up to 6 cycles of therapy as described in Section 5.3. Bone marrow examination and radiographic disease assessment will be performed at screening, the end of treatment, and 6 months post-end of treatment. If during treatment and prior to completion of 6 cycles of therapy, blood counts are consistent with CR for at least 4 weeks, an interim disease assessment may be performed at the discretion of the investigator. If a CR without MRD is documented, treatment will be discontinued. For any other response, treatment should be continued to complete 6 cycles of therapy, with the full disease assessment repeated at EOT (Table 10-2).

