#### **13.4.1.3 Time to Response**

Time to response will be measured from the start of moxetumomab pasudotox administration to the first documentation of response (CR or PR). Descriptive statistics of time to response (median, minimum, and maximum) will only be summarized for subjects who have achieved objective response.

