#### **13.4.1.4 Duration of Objective Response**

Duration of objective response will be measured from the first documentation of objective response to the event of relapse as defined in Section 11.1. Duration of objective response will be censored on the date of last disease assessment for subjects who have no documented relapse prior to data cutoff, dropout, or the initiation of alternative anticancer therapy. Duration of objective response will be summarized descriptively by using minimum and maximum of duration of objective response observed at a certain follow-up period. The proportion of subjects with response at certain time points (eg, 6 month, 1 year, or 2 year) and the median duration of response may be estimated, if feasible, for the subgroup of subjects with objective response using the Kaplan-Meier method.

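### For patients with abnormal nodes, liver or spleen at baseline, PR is dated from blood counts in Section 11.1 but from first documentation in Section 13.4.1, so one patient can have two PR onset dates

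*Protocol*

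**What the plan says.** Section 11.1 (Partial Response) opens with "PR requires all of the following for a period of at least 4 weeks". The listed criteria apply only where the feature was abnormal before treatment. For nodes, the criterion is a 50% or greater "reduction in lymphadenopathy by CT or MRI, based on sum of products of perpendicular diameters, or resolution to size consistent with CR"; a parallel criterion covers the liver and spleen. The last bullet sets the onset date: "The beginning of PR will be considered the beginning of the 4-week duration of required blood counts meeting PR criteria". It does not mention the scan.

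Section 13.4.1.4 uses a different start: "Duration of objective response will be measured from the first documentation of objective response". Section 13.4.1.3 likewise stops the time-to-response clock when CR or PR is first documented. Neither section says that, for PR, this means the count-based date.

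On scans, Section 11 states: "Bone marrow examination and radiographic disease assessment will be performed at screening, the end of treatment, and 6 months post-end of treatment". The interim assessment in Section 3.3.3 is optional and needs at least 4 weeks of CR-level counts. Its imaging may be put off to the end of treatment if the result falls short of CR without MRD.

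**The concern.** A patient with splenomegaly or enlarged nodes at baseline cannot be shown to be in PR without a scan. Section 11.1 nevertheless starts that PR on the first day of adequate counts, which may fall months before any post-baseline scan. Section 13.4.1 starts it when response is first documented. The two rules give the same patient different durations of response and different times to response.

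The count date also adds time in which the event cannot occur. Section 11.1 reserves progressive disease for the treatment period and assigns relapse only once therapy has ended. Section 13.4.1.4 counts only relapse. For a patient called PR at end of treatment, the stretch between count onset and the scan is therefore event-free by construction.

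Duration of response is a named secondary objective (Section 1.2). CR is dated from the time all its criteria are met, so duration of objective response would mix two kinds of clock.

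**Working it through.** The protocol states no figure for the gap, so there is none to reproduce. The check is calendar arithmetic.

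**Inputs**
- Cycle length 28 days, up to 6 cycles (Section 5.1.1).
- Timing of the assessment, from Table 10-2: "End of treatment is 28-42 days after the first dose of the last cycle".
- Scans required at screening, end of treatment and 6 months later (Section 11). Most of Table 10-1 is redacted in the public copy, so the on-treatment schedule is taken from Sections 3.3 and 11, which list no required scan during treatment.
- First day of qualifying counts: an assumption, varied below.

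**Formulas**
- End-of-treatment study day = 1 + 28 × (cycles − 1) + (28 to 42).
- Gap = end-of-treatment day − first day of qualifying counts.

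Six cycles without delay: 1 + 28 × 5 = 141, so end of treatment falls on Day 169 to 183. Three cycles: 1 + 28 × 2 = 57, so Day 85 to 99.

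| Cycles | Counts qualify from | Gap to scan (days) |
|---|---|---|
| 6 | 4 weeks before the scan | 28 |
| 6 | Day 85 | 169 − 85 = 84 to 183 − 85 = 98 |
| 6 | Day 29 | 169 − 29 = 140 to 183 − 29 = 154 |
| 6 | Day 15 | 169 − 15 = 154 to 183 − 15 = 168 |
| 3 | Day 29 | 85 − 29 = 56 to 99 − 29 = 70 |

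The 28-day row is the minimum when the 4-week run is complete by the scan. An interim scan would shorten the gap, and dosing delays would lengthen it.

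**Effect on one patient.** With six cycles and counts qualifying from Day 15 or Day 29, time to response is 14 or 28 days (2 or 4 weeks) by the count date. By the scan date it is 168 to 182 days (24 to 26 weeks). Duration of objective response differs by the gap in the table.

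**What first documentation means.** For CR, Section 13.4.1.1 lists imaging, marrow and counts as the elements of documentation, and the CR duration paragraph of Section 11.1 starts when all criteria are achieved. By that usage, a PR that depends on a scan is not documented until the scan. Section 11.1 also has clinical response recorded before each cycle, but without imaging that record cannot establish PR in these patients.

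**The case against.** **The specific rule could govern the general one.** The last PR bullet defines when PR begins, so Section 13.4.1 could be read as borrowing that date. The 4-week period could also mean the 4 weeks just before the assessment, a gap of about 28 days. Both readings are possible, but neither is written down, and even the second puts onset before documentation. Section 13.1 leaves analysis details to the statistical analysis plan. That plan could settle the matter, but only by saying which of the two protocol statements prevails.

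**A scan date is not the true onset either.** Shrinkage happens at an unknown time between screening and the scan, so dating PR at the scan gives the latest possible onset, and time to response then partly follows the visit schedule. This stands, and it is why the count date is worth keeping as a sensitivity analysis.

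**Guaranteed time is not confined to these patients.** Because relapse is assigned only after therapy ends, on-treatment time is event-free for PRs that rest on counts alone as well. This also stands; the proposed rule does not change it.

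**The consequence is limited.** The affected endpoints are secondary, in a single-arm trial, and Section 13.4.1.4 makes the Kaplan-Meier estimates conditional on feasibility. This stands and bounds the importance of the point.

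**Conclusion.** The two onset rules conflict for patients whose PR depends on imaging. The gap is about 28 days at the low end, 84-98 days in a middle case and 140-168 days for early count recovery with six cycles and no delay. It is shorter with fewer cycles or an interim scan. These figures assume that PR is established at the end-of-treatment scan and that the run of counts is unbroken. Patients who later reach CR are affected too if an earlier count-dated PR is taken as their first objective response.

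Four stronger readings are not supported:
- A reader might infer that PRs in general are backdated by about 5 months. That figure is near the upper end without delays and applies only with abnormal baseline imaging. For other patients, PR rests on counts and the backdating is the 4-week confirmation period.
- A reader might infer a known inflation of the median or the 6-month proportion. The protocol does not give the share of patients with abnormal baseline imaging or the timing of count recovery, so neither can be derived.
- A reader might infer that 4 weeks of size reduction must be shown and cannot be at end of treatment. The opening line allows that reading, but the onset bullet ties the 4-week period to blood counts.
- A reader might infer that the main result is at risk. The durable CR endpoint, CR rate, CR duration and ORR do not use the PR onset date, and PFS and TTF start at first dose.

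**What to change.** Replace the last PR bullet in Section 11.1 with: PR begins on the later of (a) the first day of the 4-week period of qualifying counts and (b) where nodes, liver or spleen were abnormal at baseline, the date of the first scan meeting the PR size criteria. State in Sections 13.4.1.3 and 13.4.1.4 that this is the PR date used, and report the count-based date as a sensitivity analysis.

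The cost is a few sentences and one extra analysis, with no new assessments. The downside is that duration of response will read shorter and time to response longer for these patients, and the latter will partly reflect the scan schedule.
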